4.5.3.2. Vital Signs

Weight recorded at each ZOSTER-073 study visit and change from baseline for each individual will be presented in a listing. See Section 4.1.2 for definitions of baseline for each study phase.

4.5.3.3. Zoster Brief Pain Inventory

A listing of subjects reporting pain caused by shingles in the last 24 hours on the Zoster Brief Pain Inventory (ZBPI) will be provided. Pain ratings and along with the areas of pain will be included in the listing.

4.5.3.4. HZ Episodes

Suspected episodes of HZ will be identified via the HZ episode status eCRF.

Confirmed episodes of HZ will be identified via Polymerase Chain Reaction (PCR) test on HZ lesion sample.

The number of subjects with HZ episodes will be tabulated as follows:

- From ZOSTER-041 last visit (Month 13) to ZOSTER-073 Day 1
- From ZOSTER-073 Day 1 through ZOSTER-073 study Month 24
- From first revaccination up to study end

The number and percentage of non-revaccinated subjects reporting the occurrence of HZ episodes from visit 3 (Month 24) up to study end will also be presented.

All suspected and confirmed HZ episodes occurring between the end of ZOSTER-41 and ZOSTER-073 enrollment and occurring after ZOSTER-073 will be listed.

Immunosuppressive therapies before, during, and after the episode will be listed for subjects with HZ episodes in the concomitant medications listing.

GMCs of anti-gE antibody and CD4+T-cells secreting at least 2 activation markers in subjects who had suspected and/or confirmed HZ episodes will be displayed graphically. Values taken before and after the episode will be indicated using different colors and symbols in the figure.

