7.6. **Intercurrent medical conditions that may lead to elimination of a subject from per-protocol analyses**

At each study visit, it must be recorded if the subject has experienced or is experiencing any intercurrent medical condition (IMC) that may lead to elimination from per protocol analysis. If it is the case, the condition(s) must be recorded in the eCRF.

IMCs are clinical events occurring in the course of the study which might alter or confound the interpretation of the immunologic (not safety) assessments of the protocol. With regards to humoral gE assessments, this includes any clinical event that might increase or decrease the level of anti-gE antibodies, such as protein losing conditions in which the loss of gamma-globulin or total proteins might underestimate the subject's gE response (e.g. protein loss conditions associated with proteinuria). Additional examples would be conditions that would cause the administration of exogenous anti-gE antibodies, resulting in an overestimate the subject's anti-gE response, such as conditions requiring the use of immunoglobulin (IV Ig) or blood products. For the CMI assessments, IMCs would be active viral infections that may alter CD4+ T cell counts and/or responses. Examples, although not exhaustive, of such acute viral infections would include acute Hepatitis A, acute Hepatitis B, new onset human immunodeficiency virus (HIV), and potentially acute cytomegalovirus (CMV) and/or Epstein Barr virus (EBV) infections.

The occurrence of an episode of HZ is an IMC, as the anti-gE antibody formed during active shingles in response to reactivation of VZV cannot be distinguished from the anti-gE antibody formed in response to vaccination. At Visit 1, all subjects will be informed of the signs and symptoms of typical HZ, provided a HZ-specific diary card and ZBPI questionnaire, and instructed to call for an appointment if HZ develops. The reporting period for cases of HZ will be from enrollment visit to study end. HZ cases will be collected in HZ specific screen in the eCRF. Note that all suspected or confirmed HZ that occurred since the primary follow-up study ZOSTER-041 will be collected retrospectively as part of the medical history.

ZOSTER-073 IMCs will be reported either as AE or SAEs (as appropriate) in the eCRF from enrollment visit (Visit 1) up to study end (Visit 7).

7.7. **Contraindications to subsequent vaccine administration**

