8.4.8. Evaluation and confirmation of suspected HZ cases**8.4.8.1. Suspected Herpes Zoster**

Suspected HZ is defined as a new rash characteristic of HZ (i.e. unilateral, dermatomal and accompanied by pain broadly defined to include allodynia, pruritus or other sensations), or a vesicular rash suggestive of VZV infection regardless of the dermatomal distribution and without alternative diagnosis.

Additionally, sometimes HZ cases do not present with the characteristic HZ or VZV rash, but have a clinical presentation and specific laboratory findings* suggestive of VZV infection. These cases should also be considered as occurrences of HZ.

* Specific laboratory findings include VZV-positive polymerase chain reaction (PCR) culture, immunohistochemistry, or other tests that strongly suggest VZV-infection, which have been performed in the course of a medical evaluation.

A suspected case of HZ is to be evaluated in the clinic by the investigator, within days of onset, ideally while vesicles or ulcerations are present.

Complications of HZ include, but are not limited to, PHN, HZ vasculitis, disseminated disease, ophthalmic disease, neurologic disease, and visceral disease.

The occurrence of HZ and/or HZ complications will constitute an AE/SAE, as appropriate. The occurrence of HZ is also an intercurrent medical condition (IMC) (see section 7.6).

CONFIDENTIAL

212340 (ZOSTER-073 EXT:041 Y4-10)
Protocol Amendment 1 Final

The reporting period for events of HZ will be from Visit 1 (Day 1) to study end (Month 49). At Visit 1, all subjects will be informed of the signs and symptoms of typical HZ.

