The time period for collecting and recording of IMCs (including HZ) will begin at the enrollment visit [Visit 1 (Day 1)] and will end at the last study visit [Visit 7 (Month 49)]. See section [12.5.10.5](#) for instructions on reporting of HZ.

CONFIDENTIAL

212340 (ZOSTER-073 EXT:041 Y4-10)

Protocol Amendment 1 Final

Of note, any medical events that occurred since the ZOSTER-041 last study visit (Month 13) up to study ZOSTER-073 Visit 1 (Day 1) will be recorded in medical history section on the eCRF and should not be reported via expedited reporting.
(Amended: 15 June 2020)

Evaluation of adverse events and serious adverse events

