4.3.2.1. Long-term follow-up phase

The results for the analysis of safety in the long-term follow-up phase will be tabulated as follows:

- Number and percentage of subjects reporting at least one SAE related to primary vaccination in study ZOSTER-041 classified by Medical Dictionary for Regulatory Activities (MedDRA) Primary System Organ Class (SOC) and Preferred Term (PT) from the day after

ZOSTER-041 last study visit (Month 13) to ZOSTER-073 pre-revaccination (Visit 3 Month 24) will be tabulated with exact 95% CI.

- Number and percentage of subjects with at least one suspected or biopsy-proven allograft rejection from ZOSTER-041 last visit (Month 13) to ZOSTER-073 Day 1 will be tabulated with exact 95% CI.
- Number and percentage of subjects with at least one biopsy-proven allograft rejection from ZOSTER-073 Day 1 to ZOSTER-073 pre-revaccination (Visit 3 Month 24) will be tabulated with exact 95% CI.
- Number and percentage of subjects with suspected or confirmed HZ cases from ZOSTER-041 last visit (Month 13) to study ZOSTER-073 Day 1 will be tabulated with exact 95% CI.
- Number and percentage of subjects with confirmed HZ cases from ZOSTER-073 Day 1 through ZOSTER-073 study Month 24 will be tabulated with exact 95% CI.
- Listing of subjects with history of suspected allograft rejection or history of biopsy-proven allograft rejections from ZOSTER-041 last study visit to ZOSTER-073 Day 1 will be provided.
- Listing of subjects with biopsy-proven allograft rejections from ZOSTER-073 Day 1 onward will be provided.
- Listing of subjects with a suspected or confirmed HZ episode from ZOSTER-041 last study visit to ZOSTER-073 Day 1 will be provided.
- Listing of subjects with a confirmed HZ episode from ZOSTER-073 Day 1 onward will be provided.
- Number of subjects with declining allograft function (following HZ and allograft rejection episodes), as determined by fold change from baseline serum creatinine measurements, for the time period from study ZOSTER-041 last visit (Month 13) to study ZOSTER-073 Visit 3 (Month 24). This serum creatinine fold change from baseline will be summarized descriptively. A list of subjects with an increase in serum creatinine will also be presented. Allograft dysfunction is defined as having a fold increase in serum creatinine of 1.2 or greater from the reference timepoint.

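### SAP 4.5.3.4 applies one herpes zoster identification rule to all periods, but the rule does not name the Visit 1 medical history, where the protocol records zoster from the gap between the two studies

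*SAP*

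**What the plan says.** SAP 4.5.3.4 gives one source for each class of case: "Suspected episodes of HZ will be identified via the HZ episode status eCRF", and "Confirmed episodes of HZ will be identified via Polymerase Chain Reaction (PCR) test on HZ lesion sample". It then counts subjects with HZ in three periods, the first being "From ZOSTER-041 last visit (Month 13) to ZOSTER-073 Day 1". No separate source is given for that period.

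The gap count is a secondary safety endpoint (Protocol section 4, SAP 1.1). SAP 4.3.2.1 plans its table, "Number and percentage of subjects with suspected or confirmed HZ cases from ZOSTER-041 last visit (Month 13) to study ZOSTER-073 Day 1", with an exact 95% CI and a listing, but does not say how a case is found.

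The protocol separates the two periods. Section 7.6 says of the study itself that "HZ cases will be collected in HZ specific screen in the eCRF", while HZ since ZOSTER-041 "will be collected retrospectively as part of the medical history". Section 8.4.8.1 adds: "The reporting period for events of HZ will be from Visit 1 (Day 1) to study end (Month 49". Section 12.5.9.1 says that medical events between the two studies "will be recorded in medical history section on the eCRF and should not be reported via expedited reporting". Section 8.1.3 also lists suspected or confirmed HZ under the Visit 1 medical history.

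**The concern.** A rule that fits HZ arising during ZOSTER-073 is applied to a period before enrolment, and both of its routes appear to point away from the place where the protocol puts the data. A subject who reports at Visit 1 an episode of shingles from the gap has it entered in medical history. That subject has no study lesion sample and, on the protocol's description, no entry in the HZ-specific screen. A programmer who follows 4.5.3.4 to the letter could leave the subject out of the gap table.

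At stake is the count for a named secondary endpoint over an interval of several years, shown with an exact interval that gives no sign of incomplete ascertainment. From Day 1 onward the same paragraph has a second fault: confirmation by PCR alone leaves out the protocol's other route, the HZ Ascertainment Committee (HZAC).

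**Working it through.** The documents give no figure for gap-period HZ, so there is nothing to reproduce. The check is textual, followed by an illustration of size.

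**Step 1: the texts side by side**

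| Item | SAP 4.5.3.4 | Protocol |
|---|---|---|
| Source of gap-period HZ | HZ episode status form | Visit 1 medical history (7.6, 8.1.3, 12.5.9.1) |
| HZ reporting period | Form used for all three periods | Visit 1 to Month 49 (8.4.8.1) |
| Schedule of activities at Visit 1 | Not addressed | Medical history row names HZ; row for relevant HZ information is first marked at Visit 2; general intercurrent-conditions row, which mentions HZ, is marked at Visit 1 |
| Lesion samples | PCR needed for confirmation | Event-driven, at ad-hoc visits after enrolment (8.3.2.2) |
| Confirmation | PCR only | PCR at the sponsor's or a designated laboratory; HZAC if PCR is not definitive or there is no sample (8.4.8.2, 12.2.2) |

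A gap episode therefore cannot have a study PCR result. Whether it can appear on the HZ episode status form depends on what that form holds, which the documents do not show.

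**Step 2: the HZAC route.** Under Protocol 8.4.8.2 the HZAC decides when all samples are inadequate or none exist, including HZ without a typical rash. Protocol 8.1.16 allows suspected HZ to be evaluated by video call during special circumstances, so cases without a sample are foreseeable. A case confirmed by the HZAC is confirmed under the protocol but not under SAP 4.5.3.4.

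**Step 3: scope of the gap data.** Protocol 7.6 and 8.1.3 collect all suspected or confirmed HZ. The itemised list in 12.5.9.1 names only gap episodes regarded as serious adverse events. The three sections agree on where the data go, but not on which cases are collected.

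**Step 4: illustration of size.** Inputs:
- Subjects: 68 (SAP Table 1).
- Gap: the SAP 1.2 timeframes put Visit 1 at 3.5 to 6.5 years after primary dose 2, and ZOSTER-041 Month 13 is 12 months after that dose. The gap is 3.5 − 1 = 2.5 to 6.5 − 1 = 5.5 years.
- HZ rate in renal transplant: 24.4 and 28 per 1000 person-years (Protocol 3.2.2).
- Vaccine efficacy (VE): 0%; 68%, which Protocol 3.1 reports for autologous stem cell transplant recipients; and 90% to show the range. All three are assumptions here.

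If every gap case were missed, the table would show 0/68. The Clopper-Pearson upper limit is 1 − 0.025^(1/68) = 5.3%. For comparison, 2/68 is 2.9% (0.4 to 10.2) and 5/68 is 7.4% (2.4 to 16.3).

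Expected episodes = 68 × gap × rate × (1 − VE), and the Poisson probability of a true zero is exp(−expected):

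| VE | Low: 2.5 y, 24.4/1000 | High: 5.5 y, 28/1000 | P(true zero) |
|---|---|---|---|
| 0% | 68 × 2.5 × 0.0244 = 4.148 | 68 × 5.5 × 0.028 = 10.47 | 0.016 or less |
| 68% | 4.148 × 0.32 = 1.33 | 10.47 × 0.32 = 3.35 | 0.27 to 0.04 |
| 90% | 4.148 × 0.10 = 0.41 | 10.47 × 0.10 = 1.05 | 0.66 to 0.35 |

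At 68% or 90% efficacy a true zero would not be surprising, so a zero caused by the wrong data source might pass unnoticed.

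**The case against.** The strongest reply is that the SAP plainly means to capture gap cases. SAP 4.3.2.1 has a dedicated table and listing with no restriction on source. SAP 4.5.3.4 itself lists suspected and confirmed episodes between the two studies. SAP 6.1.2 lists medical history since ZOSTER-041. Code 2060 in SAP 3.1 refers to clinically diagnosed suspected HZ before Visit 1 and PCR-confirmed HZ after it. An empty table beside a listing that contains shingles would be visibly inconsistent, and the choice of input form is often left to programming specifications.

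Much of this stands. A reader might infer that the gap endpoint must come out as zero. The documents do not support that: the SAP names a route without calling it the sole route, and the HZ episode status form may or may not hold earlier episodes reported at Visit 1. A reader might also infer that an empty table would count as evidence of long-term protection. The study is uncontrolled and descriptive, and Protocol 8.2 marks efficacy assessments as not applicable.

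The reply does not remove the mismatch. None of the other sections says how a gap case is to be identified for the table. SAP 4.5.3.4 is where the identification rule stands, and it conflicts with the protocol's recording rule. Code 2060 shows that the authors knew the source of evidence differs before and after Visit 1, but 4.5.3.4 does not carry the distinction. This is a stated rule that points to the wrong place, not merely a missing detail.

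**Conclusion.** The point holds in this form: the identification rule in SAP 4.5.3.4 does not name the medical history as the gap-period source. Read literally, it cannot confirm any gap case and could miss some or all suspected ones, contrary to the intent of SAP 4.3.2.1 and code 2060. From Day 1 onward, its PCR-only wording would drop cases that the HZAC confirms.

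The number of gap cases missed cannot be derived from the documents. The worst case is 0/68 (exact 95% CI 0 to 5.3%). The expected 4.1 to 10.5 cases with no vaccine effect, or 1.3 to 3.4 at 68% efficacy, are illustrative and do not estimate the loss. They apply rates measured from transplantation to subjects years later (one cohort's mean renal onset was 15.5 months), give all 68 subjects the same gap, borrow efficacy from another population, and count episodes where the table counts subjects. The textual mismatch does not depend on them. The correction should be made before the final analysis.

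**What to change.** In SAP 4.5.3.4, with a cross-reference from 4.3.2.1, state the source by period:

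- **ZOSTER-041 Month 13 to ZOSTER-073 Day 1:** identify suspected or confirmed HZ from the Visit 1 medical history section. Say which terms and onset dates qualify, and that confirmed here means clinically confirmed, not confirmed by study PCR. Use the same source for the table and the listing.
- **Day 1 onward:** use the HZ episode form for suspected cases. Replace PCR-only confirmation with the protocol's rule, which is PCR when definitive and the HZAC classification otherwise.

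Separately, reconcile Protocol 12.5.9.1 (gap HZ regarded as serious adverse events) with 7.6 and 8.1.3 (all suspected or confirmed HZ), and state in the report which scope the sites followed.

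The SAP change costs a few sentences and one more input dataset, and needs no new data collection.

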8.4.8.2. Confirmed HZ

A suspected case of HZ can be confirmed in two ways:

- **By Polymerase Chain Reaction**

Whenever possible, HZ lesion samples will be collected from subjects clinically diagnosed as having a suspected case of HZ (see section [8.1.15](#)). The samples will be transferred to GSK or a validated laboratory designated by GSK and tested using standardised and validated procedures for laboratory diagnosis of HZ by PCR.

Refer to section [12.2.1](#) for details of PCR assay to be performed on HZ lesion samples.

Refer to section [12.2.2](#) for details of the PCR testing algorithm to classify suspected cases of HZ.

- **By the HZ Ascertainment Committee**

All suspected HZ cases not confirmed by PCR will be referred to the HZ Ascertainment Committee (HZAC). The HZAC will classify all referred cases as either “HZ” or “not HZ”. However, the HZAC classification will serve as the final case definition only when the case cannot be confirmed or excluded by PCR results obtained by GSK or a validated laboratory designated by GSK, e.g., when all samples from a given subject are inadequate (as when both VZV and β -actin PCR results are negative), or when no samples are available for a given subject (including when suspected HZ occurs in the absence of a characteristic HZ or VZV rash). Therefore, definitive PCR results obtained by GSK or a validated laboratory designated by GSK, when available, will determine the final HZ case assignment. In such cases, the HZAC classification will not contribute to HZ case determination decision.

The HZAC will consist of physicians with HZ expertise. HZAC members, participating as investigator in this study, will not evaluate cases from their own study site. For every such case, each reviewing HZAC member will be asked to make a clinical determination of whether the case is HZ, based on review of the available clinical and laboratory information from the study site (e.g., summary of the rash and pain evaluations, digital photographs of the subject's rash, clinical progress notes and site laboratory information). A case will be considered as “HZ” if the HZAC members concur unanimously; otherwise, it will be classified as “not HZ”. As described above, the HZAC case assignment will only be considered as the final case assignment if definitive PCR results obtained by GSK or a validated laboratory designated by GSK are not available. Further details will be provided in the HZAC charter.

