Please note that PCR test results or HZAC classification as described above will not serve as the final case definition if the following applies.

CONFIDENTIAL212340 (ZOSTER-073 EXT:041 Y4-10)
Protocol Amendment 1 Final

Cases of suspected HZ will not be considered a confirmed case of HZ if they potentially could constitute a primary VZV infection (varicella).

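### SAP 4.5.3.4 gives PCR as the only route to a confirmed zoster case, whereas the protocol also confirms by committee and bars possible varicella; SAP 4.8 declares no change

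*SAP*

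**What the plan says.** **SAP.** Section 4.5.3.4 takes suspected episodes from an eCRF page and then gives the rule for confirmation: "Confirmed episodes of HZ will be identified via Polymerase Chain Reaction (PCR) test on HZ lesion sample". The readable SAP text mentions neither the HZAC nor varicella. The same section introduces its tabulations with "The number of subjects with HZ episodes will be tabulated as follows", followed by three time windows, without saying whether confirmed or all episodes are counted. It also promises a full listing: "All suspected and confirmed HZ episodes occurring between the end of ZOSTER-41 and ZOSTER-073 enrollment and occurring after ZOSTER-073 will be listed".

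Section 4.3.2.1 plans a count of confirmed HZ from Day 1 to Month 24 with an exact 95% CI. Sections 4.3.2.1 and 4.3.2.2 plan listings of confirmed episodes, and a note closing 4.3.2.2 says that the listings hold all events. Section 4.8 declares two departures from the protocol: the analysis set for non-revaccinated subjects, and the period and source of SAEs related to primary vaccination. Neither concerns HZ.

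**Protocol.** Section 8.4.8.2 opens with "A suspected case of HZ can be confirmed in two ways": PCR, or the HZAC. Of the second route it says that "the HZAC classification will serve as the final case definition only when the case cannot be confirmed or excluded by PCR results". The examples it gives are inadequate samples and no samples, "including when suspected HZ occurs in the absence of a characteristic HZ or VZV rash". It then sets a condition above both routes: "PCR test results or HZAC classification as described above will not serve as the final case definition if the following applies". The condition is that the case could be a primary varicella infection. Section 12.2.2 repeats the sequence of PCR first and HZAC second, but not the varicella condition.

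**The concern.** Confirmed HZ is a secondary safety endpoint in SAP 1.1, from Day 1 to Month 24 in all subjects and from the first revaccination dose to study end in revaccinated subjects. The endpoint is carried over from the protocol, but the rule that decides who counts is narrower in one respect and looser in another. A programmer who follows SAP 4.5.3.4 would produce a count that is not the one the protocol defines, and a reader of the report would not be told.

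The HZAC route has a real use. The protocol recognises HZ without the characteristic rash (8.4.8.1), where there may be no lesion to swab. It asks for lesion samples only when possible (8.4.8.2). Under special circumstances it allows virtual evaluation and forbids samples that cannot be processed or stored in time (8.1.16).

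**Working it through.** The plan gives no figure to reproduce here. The check is a comparison of the two rules, followed by the scale of one case.

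**1. The rules side by side**

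| Suspected case | Protocol 8.4.8.2 and 12.2.2 | SAP 4.5.3.4 as written |
|---|---|---|
| At least one sample VZV-positive, varicella not in question | Confirmed | Confirmed |
| All samples VZV-negative, at least one beta-actin positive | Not HZ | Not confirmed |
| All samples inadequate, or no sample; HZAC unanimous for HZ | Confirmed | Not confirmed |
| All samples inadequate, or no sample; HZAC not unanimous | Not HZ | Not confirmed |
| PCR-positive, possible primary varicella | Not confirmed | Confirmed |

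The rules disagree in the third and fifth rows. The third lowers the SAP count and the fifth raises it.

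**2. Where the difference lands**

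- *Last ZOSTER-041 visit to Day 1.* SAP 1.1 and 4.3.2.1 count suspected or confirmed cases together, so the confirmation rule matters little.
- *Day 1 to Month 24.* SAP 4.3.2.1 counts confirmed cases only, with an exact CI. An HZAC-confirmed case is lost from it.
- *First revaccination to study end.* SAP 4.3.2.2 plans a listing, and the count comes from 4.5.3.4. The window matches the confirmed-HZ endpoint in SAP 1.1, so count and endpoint can be paired. If the count is of confirmed cases, the same loss applies.
- *Listings.* The episode appears, but would not be classed as confirmed. The columns described at the end of 4.3.2.2 show timing, not the route of confirmation.

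**3. Scale of one case**

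Inputs: 68 subjects enrolled (SAP 1.2, Table 1) and the Clopper-Pearson interval (SAP 4.1.1).

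- One case: 1/68 = 1.47%, about 1.5 percentage points.
- 0/68: upper limit 1 − 0.025^(1/68) = 5.28%, so 0% (0 to 5.3%).
- 1/68: lower limit 1 − 0.975^(1/68) = 0.037%; upper limit, the 97.5th percentile of Beta(2, 67), = 7.92%. So 1.5% (0.04 to 7.9%).

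After revaccination the denominator is the Exposed Set. Its size is not given, but it cannot exceed the enrolled number, so one case is at least 1/68 there.

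**The case against.** The best reply is that SAP 4.5.3.4 does not contain the word *only*. Its sentence parallels the one naming the eCRF page for suspected episodes and may be a note on data sources. The SAP is based on Protocol Amendment 1 and keeps the endpoint unchanged, and final case assignment is made upstream under an HZAC charter. Silence in 4.8 therefore fits incomplete shorthand as well as a new definition. That is fair about intent. It does not repair the text, because the section names one route and cites neither protocol section.

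Three further points stand:

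- **Varicella.** Protocol 12.2.2 also omits the exclusion, and nothing in the documents suggests that such a case is likely here.
- **Missing samples.** Protocol 8.1.16 also allows collection away from the site, and 8.1.15 asks for a return visit when adequate samples cannot be taken. How often PCR will not be definitive is unknown.
- **No test is affected.** All analyses are descriptive (SAP 2.1).

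A reader might infer more than the documents support:

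- *That HZAC-confirmed cases vanish from the report.* They do not. The closing note in 4.3.2.2 and the listing in 4.5.3.4 keep every episode visible.
- *That the non-revaccinated count after Month 24 fails to match its endpoint.* In SAP 1.1 the later confirmed-HZ endpoint is for revaccinated subjects only, so there is no such endpoint to match.
- *That the error is a large share of all cases.* Over 68 × 2 = 136 person-years, the renal transplant rates in protocol 3.2.2 give 136 × 24.4/1000 = 3.32 to 136 × 28/1000 = 3.81 cases with no vaccine effect, and one case is 26 to 30% of that. But this presupposes one affected case and borrows rates from other cohorts. It also assumes two full years each, which delayed enrolees with Visits 1 and 2 on the same day may not provide.

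**Conclusion.** The wording gap is established from the text with high confidence. SAP 4.5.3.4 omits the HZAC route and the varicella exclusion, and 4.8 does not declare the change. Read literally, this changes the confirmed-HZ count and its CI from Day 1 to Month 24, any confirmed-only count after revaccination, and the confirmed label in the listings.

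The supportable size is about 1.5 percentage points per affected case, taking the 68 enrolled as the denominator. The number of affected cases may be zero; the documents do not let one estimate it. The consequence is a descriptive safety figure that departs from its protocol definition without notice. It should be corrected, but it does not threaten the primary antibody endpoints.

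**What to change.** In SAP 4.5.3.4, define confirmed HZ by the protocol's final case classification: the definitive PCR result where there is one, otherwise the HZAC decision, with possible primary varicella excluded. Cite both 8.4.8.2 and 12.2.2, since only the former carries the varicella exclusion. Use that classification for the count in 4.3.2.1 and to mark confirmed status in the listings. State for each tabulation in 4.5.3.4 whether it counts confirmed or all episodes. If confirmation by PCR alone is intended, say so in 4.8 and justify it.

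The cost is SAP wording. The protocol already requires the HZAC classifications, so no new data are needed.
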